### **2.2.2 Dose Rationale**

Efficacy and safety data was collected from normal healthy subjects in a phase 1 trial as well as HCT recipients in a phase 2 clinical trial (VCL-CB01-101 and CB01-202, respectively). The dose used in the phase 2 study was 1 mL of 5 mg/mL and 4 doses were given over approximately a 6 month time period. The dose and dose schedule appeared to be well tolerated.

The first dose of vaccine is scheduled to be administered at -14 to -3 days prior to transplant, and within 72 hours prior to the start of conditioning therapy. The first dose is scheduled during this time frame to ensure protein expression at the time of infusion of the donor stem cells as animal models demonstrate that the peak protein expression after injection of a DNA plasmid is between 3 and 14 days. This dose is given prior to the start of conditioning therapy as protein expression may be decreased because of a catabolic state in the patient after the start of conditioning therapy. The second dose of vaccine is scheduled as close to Day 14 after transplant as possible to ensure protein expression and development of a protective immune response at the expected time of the first viremic episodes, which is approximately 30 days after transplant. Finally, doses are scheduled for 60, 90 and 180 days after transplant to help protect against late-onset viremia.

## 2.3 Variables

### 2.3.1 Primary Variable

The primary endpoint of the study is the composite of overall mortality and CMV EOD through 1 year post-transplant.

### 2.3.2 Secondary Variables

The 2 key secondary endpoints are:

- Time to first protocol-defined CMV viremia [CMV plasma viral  $\geq 1000$  IU/mL as assessed by the central laboratory] through 1 year post-transplant.
- Time to first adjudicated CMV-specific AVT through 1 year post-transplant.

Additional secondary endpoints are:

- Time to first CMV-specific AVT for protocol-defined CMV viremia [CMV plasma viral load  $\geq 1000$  IU/mL as assessed by the central laboratory] or CMV EOD through one year post-transplant.

### 2.3.3 Exploratory Variables

- Clinical outcomes:
  - Overall mortality
  - Incidence of CMV EOD
  - Incidence of Grade 3-4 aGVHD
  - Incidence of severe cGVHD
  - Incidence of grade 3 treatment-emergent viral, bacterial, or fungal infections other than CMV
  - Maximum grade of aGVHD
  - Maximum cGVHD score
  - Relapse mortality (death due to relapse of the subject's primary disease)
  - Non-relapse mortality (death due to causes unrelated to the subject's primary disease)
  - Incidence of graft rejection
  - Incidence of failure to engraft
  - Time to engraftment
  - Time to platelet recovery
  - Incidence of relapse of primary disease requiring therapy.
  - Number of episodes of protocol-defined CMV viremia [CMV plasma viral load  $\geq 1000$  IU/mL by the Abbott RealTime CMV assay as assessed by the central laboratory]
  - Time to Grade 3 treatment-emergent viral, bacterial, or fungal infections other than CMV
- Duration of hospitalization(s)
- Health economic/resource utilization

- Subjects' quality of life (QOL) variables (EQ-5D, Functional Assessment of Cancer Therapy – Bone Marrow Transplant [FACT-BMT], and Work Productivity and Activity Impairment Questionnaire: General Health [WPAI: GH])
- Immunogenicity variables
  - T-cell responses to pp65
  - gB-specific antibody levels

#### **2.3.4 Safety Assessments**

- Vital signs
- Adverse events (AEs)
- Local reactogenicity signs and symptoms using both the NCI-CTCAE Version 4.03 grading scale and the protocol-specified reactogenicity scale [Appendix 7](#)
- Clinical laboratory assessments as defined in [Appendix 1](#)
- Physical examination (PE)

#### **2.3.5 Pharmacogenomics (PGx) Assessment (Optional)**

An optional PGx saliva sample will be collected during the baseline visit (V2) after randomization but prior to the first dose of study drug. These may be assessed retrospectively to include:

- Exploratory analysis of the relationship between genes potentially involved in immunogenicity and response to ASP0113 in terms of efficacy and/or safety.
- Exploratory analysis of the relationship between genes of relevance to toxicity and/or safety issues and response to ASP0113 with respect to safety.

Please refer to [Appendix 19](#) (PGx Sub-Study) for additional information on the retrospective PGx sub-study associated with this study.

### **3 STUDY POPULATION**

#### **3.1 Selection of Study Population**

This study will randomize HCT recipients who are at least 18 years of age or of legal age of consent and are CMV-seropositive.

Subjects will be enrolled in the trial based on positive CMV serostatus, which will be CMV IgG antibody detection by the local laboratory. Testing will be performed prior to randomization. Presence of anti-CMV IgG antibodies will indicate a positive CMV status.

#### **3.2 Inclusion Criteria**

A subject is eligible for the study if all of the following apply:

1. Institutional Review Board (IRB)/Independent Ethics Committee (IEC)-approved written informed consent and privacy language as per national regulations (e.g., Health Insurance Portability and Accountability Act [HIPAA] Authorization for U.S. sites) must be

- obtained from the subject or legally authorized representative prior to any study-specific related procedures (including withdrawal of prohibited medication, if applicable).
2. Subject is a male or female subject who is at least 18 years old or the legal age of consent (whichever is greater).
  3. Subject is a CMV-seropositive HCT recipient as confirmed by local laboratory at screening.
  4. Subject is planned to undergo either of the following:
    - a. Sibling Donor Transplant - 7/8 HLA-A, -B, -C, -DR $\beta$ 1 match utilizing high resolution typing or 8/8 HLA-A, -B, -C, -DR $\beta$ 1 match utilizing low or high resolution typing.\*
    - b. Unrelated Donor Transplant - 7/8 or 8/8 HLA-A, -B, -C, -DR $\beta$ 1 match utilizing high resolution typing.\*

\* A minimum of 8 allele matching is required. Subjects with matches performed at more than 8 alleles are included if they have 7/8 or 8/8 match at the HLA-A, -B, -C, -DR $\beta$ 1 alleles.
  5. Subject is scheduled to receive an allogeneic peripheral blood stem cell or bone marrow transplant (BMT) for the treatment of hematologic disorders as indicated in Inclusion Criterion 6.
  6. Subject has 1 of the following underlying diseases:
    - a. Acute myeloid leukemia (AML), with or without a history of myelodysplastic syndrome (MDS), in first or second complete remission (CR) [Appendix 6](#) or in early relapse (< 20% blasts in bone marrow with no circulating blasts in peripheral blood and no extramedullary leukemia).
    - b. Acute lymphoblastic leukemia (ALL), in first or second CR [Appendix 6](#).
    - c. Acute undifferentiated leukemia (AUL) in first or second CR [Appendix 6](#).
    - d. Acute biphenotypic leukemia in first or second CR [Appendix 6](#).
    - e. Chronic myelogenous leukemia (CML) in either chronic or accelerated phase.
    - f. Chronic lymphocytic leukemia.
    - g. One of the following MDS defined by the following:
      - i. Refractory anemia with evidence of dysplasia.
      - ii. Refractory anemia with ringed sideroblasts.
      - iii. Refractory cytopenia with multilineage dysplasia.
      - iv. Refractory cytopenia with multilineage dysplasia and ringed sideroblasts.
      - v. Refractory anemia with excess blasts-1 (5%-10% blasts).
      - vi. Refractory anemia with excess blasts-2 (10%-20% blasts).
      - vii. MDS, unclassified.
      - viii. MDS associated with isolated deletion (5q).
      - ix. Chronic myelomonocytic leukemia.
    - h. Primary or secondary myelofibrosis without leukemic transformation except if Dynamic International Prognostic Scoring System category of high or intermediate-2 [Appendix 5](#).

- i. Lymphoma (including Hodgkin's) with chemosensitive disease ( $\geq 50\%$  response to chemotherapy).
  7. Female subject must be either:
    - Of non-childbearing potential
      - Postmenopausal (defined as at least 1 year without any menses) prior to screening, and if  $< 50$  years of age and not documented to be surgically sterile must have a negative urine or serum pregnancy test at screening, or
      - Documented surgically sterile or status post-hysterectomy (at least 1 month prior to screening), or
    - Or, if of childbearing potential
      - Must have a negative urine or serum pregnancy test at screening, and
      - If heterosexually active, must use at least 1 form of birth control\* (which must be a barrier method) starting at screening and through the primary study period.
  8. Female subject must not be breastfeeding at screening, through the treatment period and through the primary study period.
  9. Female subject must not donate ova starting at screening, through the treatment period and through the primary study period.
  10. Male subject and their female spouse/partners who are of childbearing potential must be using highly effective contraception consisting of 2 forms of birth control\* (1 of which must be a barrier method) starting at screening, through the treatment period and through the primary study period.
- \* Acceptable forms include:
- Consistent and correct usage of established oral contraception.
  - Established intrauterine device (IUD) or intrauterine system (IUS).
  - Barrier methods of contraception: condom or occlusive cap (diaphragm or cervical/vault caps) with spermicidal foam/gel/film/cream/suppository <Not applicable to sites in Japan: with spermicidal foam/gel/film/cream/suppository>
  - For sites in Japan: calendar-based contraceptive methods (Knaus-Ogino or rhythm method)
11. Male subject must not donate sperm starting at screening, through the treatment period and through the primary study period.
  12. Subject is willing to comply with the protocol.
  13. Subject agrees not to participate in another interventional study while on treatment. New regimens of approved chemotherapeutic drugs or antibodies, conditioning drugs, irradiation and T-cell depleting antibodies, except alemtuzumab, are allowed.

Waivers to the inclusion criteria will NOT be allowed.

### 3.3 Exclusion Criteria

A subject will be excluded from participation if any of the following apply:

1. Subject has active CMV disease or infection or has received treatment for active CMV disease or infection within 3 months (90 days) prior to transplant.
2. Subject has planned CMV prophylactic therapy with antiviral drugs or CMV-specific immunoglobulins from randomization through the primary study period completion/day 365 visit (V14).
3. Subject has a modified hematopoietic cell transplant comorbidity index (HCT-CI) score  $\geq 4$  Appendix 4.
4. Subject is known to be positive for human immunodeficiency virus (HIV), hepatitis B surface antigen or hepatitis C RNA PCR.
5. Donor CMV serostatus is unknown.
6. Subject has received any of the following substances or treatments:
  - a. Alemtuzumab within 60 days prior to transplant, including conditioning regimen. Subjects for whom treatment with alemtuzumab is planned at any time from 60 days prior to through 1 year post-transplant must not be enrolled in the trial.
  - b. T-cell depletion of donor cell product.
  - c. Administration of a CMV vaccine, including any prior exposure to ASP0113.
7. Subject has received an allogeneic stem cell transplant within 1 year prior to transplant (subjects who have received a prior autologous transplant are allowed).
8. Subject has a current malignancy in addition to the malignancy being treated for the study or the subject has a history of any other malignancy (within the past 5 years prior to screening) except non-metastatic basal or squamous cell carcinoma of the skin that has been treated successfully or cancer in situ of the cervix uteri that has been handled by local surgery.
9. Subject has an unstable medical or psychiatric condition, including a history of illicit drug(s) or alcohol abuse that the Investigator believes will interfere with protocol requirements.
10. Subject has had an allergic reaction to any component of the vaccine. Subject has had an allergic reaction to aminoglycosides as kanamycin is used in the manufacturing process of the vaccine.
11. Subject has participated in any interventional clinical study or has been treated with any investigational research products within 30 days or 5 half-lives, whichever is longer, prior to the initiation of screening. (Investigational research products are considered those products that have not been approved for any indication in the country where the subject is enrolled. New regimens of approved chemotherapeutic drugs or antibodies, conditioning drugs, irradiation and T-cell depleting antibodies, except alemtuzumab, are allowed.)

12. Subject who has received a prior HCT and has residual cGVHD.
13. Subject who is scheduled to have a cord blood transplant or a haploidentical transplant.
14. Subject has a platelet count of less than 50000 mm^3 within 3 days prior to randomization (platelet transfusions are allowed). Results received in an equivalent local unit of measure must be converted to SI units.
15. Subject has aplastic anemia or multiple myeloma.
16. For sites in Japan only: Other subjects considered ineligible by the Investigator/sub-Investigator.

Waivers to the exclusion criteria will NOT be allowed.

### **3.4 Contraception and Pregnancy Avoidance**

During the screening period of the study and at the time of randomization, a urine or serum pregnancy test will be performed on all women of childbearing potential and all women who are of non-childbearing potential but are < 50 years of age and not documented to be surgically sterile. Subsequently, urine or serum pregnancy tests will be performed on the same day and prior to each dose, at visit 13 and at the primary study period completion/ day 365 visit (V14). All pregnancy tests will be done locally. For subjects who receive mycophenolate mofetil, additional pregnancy testing must be done in accordance with local regulatory requirements.

Subjects who become pregnant or have a positive pregnancy test during the treatment period will be withdrawn from further study treatment [Section 3.5].

Female subjects or partners of male subjects who become pregnant during the study will be followed through delivery. Pregnancy of female subjects or female partners of male subjects from first dose through 1 year post-transplant will be reported as an SAE [Section 5.5.9].

### **3.5 Discontinuation Criteria for Individual Subjects**

A subject discontinued from study drug treatment is a subject who enrolled in the study and for whom study drug treatment is terminated prematurely for any reason.

A subject is free to withdraw from the study drug treatment and/or study follow-up for any reason and at any time without giving reason for doing so and without penalty or prejudice. This is referred to as withdrawal of consent if the subject does not allow efforts to be made even to assess survival status. Withdrawal of consent can only occur if it is subject-initiated.

The Investigator is also free to terminate a subject's study drug treatment at any time if the subject's clinical condition warrants it and the Investigator deems that further treatment is not in the best interest of the subject.

Study drug administration and participation in the study will continue for subjects when a non-fatal endpoint is met.

If a subject fails to receive 1 or more doses of study drug after the first injection, but is able to continue in the trial, the subject's participation in the trial should not be terminated.

#### Study Discontinuation

Subjects will be withdrawn from study and will receive no further follow-up except for mortality (at day 365 post-transplant) through public records/sources if the following occurs:

- Withdrawal of consent by subject

Subjects will be withdrawn from study and will receive no further follow-up if the following occurs:

- Subject did not receive first dose of study drug

For a subject who prematurely withdraws from the study (discontinues treatment with no continued follow-up) the study completion visit must be completed within 14 days of study withdrawal.

#### Treatment Only Discontinuation

Subjects will be withdrawn from study drug treatment if any of the following occur. However, they are to continue to be followed according to the protocol Schedule of Assessments [Table 1](#) with exception of the dose follow-up visits (i.e. V3, V6, V8, V10, and V12).

- Investigator's decision that further treatment is not in the best interest of the subject.
- Pregnancy (female subjects only).
- Failure to engraft.
- Local reactogenicity with a Grade  $\geq 3$  based on the criteria defined in [Appendix 7](#) and confirmed by a health care professional.
- Anaphylaxis with a Grade  $\geq 3$  based on NCI-CTCAE Version 4.03.
- Seizure considered possibly or probably related to study drug treatment.
- Participation in another interventional trial for an investigational research product (investigational research products are considered those products that have not been approved for any indication in the country where the subject is enrolled).

If a subject is withdrawn from study drug treatment and is unable to comply with study procedures as defined in the Schedule of Assessments, the subject must be asked if they are willing to be followed for SAEs through 30 days of last dose of study drug treatment, to attend the scheduled final study visit (V14), to be assessed for CMV EOD, and/or to be followed for mortality. They must also be asked if they are willing to be followed through the long term follow-up period.

Subjects who discontinue from the study after one or more doses of study drug will not be replaced. Subjects who are randomized but never receive study drug will be replaced, to a total of approximately 500 dosed subjects.

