9. The modified hematopoietic cell transplant-comorbidity index (HCT-CI) score are to be completed during screening with history and laboratory from the screening visit. Local laboratory results are to be used in the assessment. Local laboratories may be repeated once to score the HCT-CI. Pulmonary function tests (PFTs) including forced expiratory volume (FEV1) and diffusing lung capacity of carbon monoxide (DLco), multi gated acquisition scan (MUGA), and/or echocardiograms performed within 6 months (180 days) prior to screening are to be used for scoring pulmonary and cardiac comorbidities. PFTs (FEV1 and DLco), MUGAs /or echocardiograms not performed within 6 months of screening will have to be repeated for scoring purposes.
10. For all females of childbearing potential and all females who are of non-childbearing potential but are < 50 years of age and not documented to be surgically sterile, a urine or serum pregnancy test will be performed at screening, on the same day and prior to each dose, at visit 13, and at the primary study period completion/day 365 visit (V14). All pregnancy tests will be done locally. For subjects who receive mycophenolate mofetil, additional pregnancy testing should be done in accordance with local regulatory requirements.
11. All AEs and SAEs will be collected from signing of the informed consent through 30 days post last dose of study drug. All events requiring adjudication (CMV end organ disease [EOD], initiation of CMV-specific antiviral therapy [AVT], and cause of death), grade 3 and higher grade AEs as well as all SAEs will be collected from 31 days post last dose of drug through 1 year post-transplant. A change in medical status or medical history from time of signing of informed consent through first dose of study drug is to be reported as an AE or SAE as applicable. In this study, the day 0 HCT is not considered an AE.

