The Sponsor or Sponsor's designee will submit expedited safety reports (i.e. IND Safety Reports) to the regulatory agencies (i.e. FDA) as necessary, and will inform the investigators of such regulatory reports. Investigators must submit safety reports as required by their IRB/IEC within timelines set by regional regulations (i.e. EU, (e)CTD, FDA). Documentation of the submission to and receipt by the IRB/IEC of expedited safety reports should be retained by the site.

The Sponsor/ delegated CRO will notify all investigators responsible for ongoing clinical studies with the study drug of all SAEs which require submission per local requirements IRB/IEC/the heads of the study sites.

The heads of the study sites/investigators should provide written documentation of IRB/IEC notification for each report to the Sponsor per local requirements IRB/IEC.

The study site may contact the Sponsor's Medical Monitor/Expert for any other problem related to the safety, welfare, or rights of the subject.

***UNIQUE to studies enrolling subjects in EU:*** For SUSARs from a blinded trial, unblinded CIOMS-I report will be submitted to the authorities and IRB/IEC where required.

All observed or spontaneously reported SAEs occurring up to 12 months after transplant must be captured on the eCRFs and reported to the Sponsor (for sites in Japan: the delegated CRO) in accordance with these guidelines. All SAEs will be recorded within the source documents, on the SAE worksheets (for sites in Japan: JUTOKUNA YUUGAIJISHOU HOUKOKUSHO) which will be faxed to the Sponsor (for sites in Japan: the delegated CRO), and collected in the eCRF. AEs leading to subject discontinuation from the study will be collected in the appropriate section of the eCRF.

For the purposes of expedited safety reporting to the regulatory agencies, SAEs describing an event listed in [Appendix 3](#) as common and disease related or a protocol-defined endpoint (e.g., CMV diseases) may not be reported by Astellas for a single occurrence for a given subject. However, Astellas may report as appropriate aggregated cases of such events.

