7.4.2.1 Key Secondary Endpoint - Protocol-Defined CMV Viremia

The protocol-defined CMV viremia through 1 year post-transplant is defined as a CMV plasma viral load ≥ 1000 IU/mL by the central laboratory. The plasma viral load after transplantation through day 380 from transplantation day will be considered. A subject who has more than one time with CMV viral load ≥ 1000 IU/mL will be counted once. This endpoint will be analyzed by 2 statistical methods for FAS, mFAS and PPS-FAS.

A Cox proportional subdistributional hazards model will be used for the time-to-first protocol-defined CMV viremia through 1 year post-transplant. This model accounts for the competing risk of death, after which CMV Viremia can no longer be observed. A subject who has more than 1 incidence of having CMV viral load ≥ 1000 IU/mL will consider the first time of having this event. The Cox model will include treatment group, donor-recipient relatedness, donor CMV serostatus as factors in the model. From this model, 1 – Hazard Ratio and its 95% CI will be calculated. The p-value from this model will be calculated.

The treatment effect will also be evaluated with the following null hypothesis:

$$H_0: 1\text{-Hazard Ratio} \leq 20\%.$$

While the alternative hypothesis is:

$$H_1: 1\text{-Hazard Ratio} > 20\%.$$

The p-value for the above hypothesis tests will use a Wald statistic using the Cox model parameter estimate for the treatment effect, θ_t :

$$Z = (\theta_t - \ln(1-20\%))/S.E.(\theta_t)$$

CIFs will be used to estimate the crude incidence of CMV Viremia by treatment group while accounting for the competing risk of death.

The analysis window extends to day 380 from the transplantation day in order to accommodate the protocol allowed visit windows. If a subject's first event is after day 380, this subject will be censored on day 380 as the 1-year post transplantation is the primary

study period. A subject without an event will be censored on the last day of central laboratory assessment. In other words, if a subject has a central laboratory assessment beyond day 380 that is negative, this subject will be censored on day 380. A subject who dies prior to reporting CMV Viremia will be handled using a competing risks model.

Additionally, the same CMH method as in the primary endpoint will be used to calculate odds ratio and its 95% CI and 1-relative risk and its 95% CI. The p-value from this method will also be calculated.

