7.4.2.2 Key Secondary Endpoint of Adjudicated CMV-Specific Antiviral Therapy

Subjects' CMV-specific antiviral therapy (AVT) use will be adjudicated by the independent and blinded committee. This endpoint will be evaluated through 1 year post-transplant (i.e., through day 380 from transplantation) and will be considered as a key secondary efficacy endpoint. This endpoint will be analyzed by 2 statistical methods for FAS, mFAS and PPS-FAS.

A Cox proportional subdistributional hazards model will be used for time-to-first use of CMV-specific AVT through 1 year post-transplant. This model accounts for the competing risk of death, after which use of CMV-specific AVT can no longer be observed. If a subject used CMV-specific AVT more than once, the day of first use will be counted. If a subject did not use any CMV-specific AVT, the subject will be censored on the day of last study evaluation according to the end of study eCRF.

To evaluate the treatment effect compared to placebo, 1-Hazard Ratio, its 95% CI and p-value from the Cox model (as in Section 7.4.2.1) will be calculated.

CIFs will be used to estimate the crude incidence of CMV-specific AVT while accounting for the competing risk of death.

Additionally, the same CMH method as in the primary endpoint will be used to calculate odds ratio and its 95% CI and 1-relative risk and its 95% CI. The p-value from this method will also be calculated.

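### For subjects off drug who cannot keep the schedule, the reduced follow-up list omits CMV-specific AVT, and the SAP can then count unascertained time as AVT-free

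*Protocol*

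**What the plan says.** **Follow-up after stopping drug (Protocol 3.5, Treatment Only Discontinuation; the synopsis has the same text).** The default is full follow-up without the dose follow-up visits: "they are to continue to be followed according to the protocol Schedule of Assessments". A reduced list applies only under a further condition: "If a subject is withdrawn from study drug treatment and is unable to comply with study procedures as defined in the Schedule of Assessments". For that group, "the subject must be asked if they are willing to be followed for SAEs through 30 days of last dose of study drug treatment". The list continues with attendance at V14 and then "to be assessed for CMV EOD, and/or to be followed for mortality". Willingness to enter long-term follow-up is also asked. Neither CMV-specific AVT nor viral load is named.

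**What the protocol collects to 1 year.** Table 1 footnote 11 defines the adjudicated events: "All events requiring adjudication (CMV end organ disease [EOD], initiation of CMV-specific antiviral therapy [AVT], and cause of death". It collects them, with Grade 3 or higher AEs and all SAEs, from day 31 after the last dose to 1 year after transplant. Section 5.4.2 gives the same horizon, and section 2.2.1 has adjudicated AVT assessed to 1 year. On SAEs, section 5.5.6 says "All observed or spontaneously reported SAEs occurring up to 12 months after transplant must be captured on the eCRFs". SAP 6.2 runs the TEAE window to 1 year whatever the date of last dose.

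**How the SAP ends follow-up.** For AVT (7.4.2.2): "If a subject did not use any CMV-specific AVT, the subject will be censored on the day of last study evaluation", taken from the end-of-study form. Section 7.4.2.3.2 uses the same rule for AVT or EOD. For viremia (7.4.2.1): "A subject without an event will be censored on the last day of central laboratory assessment".

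**The concern.** Of the three adjudicated event types, the reduced list keeps EOD and death and leaves out AVT. A site that follows the list literally has no prompt to ask about AVT, although AVT is a key secondary endpoint and part of two other secondary endpoints (SAP 7.4.2.3.1 and 7.4.2.3.2).

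The SAP adds to the problem. Its AVT censoring date depends on when the subject was last evaluated for anything, not on when AVT status was last known. Take a subject who leaves the schedule at day 40 and returns only for V14. If AVT in between is not retrieved, that subject contributes about 325 days (365 − 40) of apparently AVT-free time.

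Two things are at stake. One is under-counting of AVT, with bias if the shortfall differs between arms. The other is a 1-year SAE record that may be incomplete for these subjects while the safety tables treat it as running to 1 year.

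**Working it through.** **1. The plan's own figure.** The documents give no sample size for AVT, so the only figure to reproduce is the primary one: 35.3% vs 22.5%, two-sided 0.05, 80% power. The uncorrected formula gives n′ = 195.7 per arm. The continuity correction, n = (n′/4)·(1 + √(1 + 4/(n′·0.128)))², gives 211.03, rounded up to 212 per arm, or 424 in total, as stated. Inverting it at 250 per arm gives 86.6%, against a stated 86%. The present point does not touch this figure.

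**2. The passages side by side.**

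| Item | Reduced list (3.5) | Elsewhere in the protocol | SAP end of follow-up |
|---|---|---|---|
| CMV EOD | asked | to 1 year | analysed with AVT in 7.4.2.3.2: last study evaluation |
| Death | asked | to 1 year | unknown survival counts as an event (primary) |
| CMV-specific AVT | not asked | to 1 year (2.2.1, 5.4.2, footnote 11) | last study evaluation |
| Viremia | not asked | to 1 year (5.3.1) | last central assay |
| SAEs | 30 days after last dose | 12 months after transplant (5.5.6) | TEAE window to 1 year (6.2) |

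Viremia is also absent from the list, but its censoring rule stops the clock when testing stops. For AVT the clock can keep running.

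For the CMH analyses, the SAP says only that the primary endpoint's method is used. The rule that counts unknown status as an event is written for survival, and 7.10.1 imputes no other variables. That unascertained AVT becomes a non-event is therefore an inference from silence, though the natural one.

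**3. Size if both arms are affected equally.** Inputs: phase 2 AVT rates of 61.8% (placebo) and 47% (ASP0113) from Protocol 1.3.2.2, and 250 per arm. Assumed, because the documents are silent: a share d of each arm on the reduced list, and a fraction u of their AVT starts unrecorded. Observed rate = true rate × (1 − d·u). Power = Φ[(√n·Δ − 1.96·√(2p̄(1−p̄))) / √(p₁q₁ + p₂q₂)].

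Full capture: Δ = 0.148 and p̄ = 0.544, so (2.340 − 1.381)/0.6965 = 1.378, giving 91.6%.

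| d | power, u = 0.5 | power, u = 1 |
|---|---|---|
| 5% | 90.1% | 88.4% |
| 10% | 88.4% | 84.8% |
| 20% | 84.8% | 76.3% |

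The factor (1 − d·u) cancels in the relative risk, which stays at 0.47/0.618 = 0.76. The cost here is power, not bias in that ratio.

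**4. Size if only one arm is affected.** This was simulated with no true effect: 250 per arm, 61.8% AVT in both arms, 70% of starts on days 14–60 and the rest by day 365, no competing death, ordinary Cox model, 300 runs. A share of one arm loses AVT ascertainment from the day shown. The table gives the apparent hazard ratio of that arm to the other.

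| Share of one arm | Lost from day 30, carried to day 365 | Same, censored at day 30 | Lost from day 60, carried to day 365 | Same, censored at day 60 |
|---|---|---|---|---|
| 5% | 0.94 | 1.01 | 0.99 | 1.00 |
| 10% | 0.90 | 0.99 | 0.97 | 0.99 |
| 20% | 0.80 | 1.00 | 0.93 | 0.99 |

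The affected arm always looks better. If it is placebo, the ASP0113-to-placebo ratio is the reciprocal (for example 1/0.80 = 1.25). Censoring at the last ascertainment removes the artefact here because loss was simulated as unrelated to AVT risk.

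**The case against.** The strongest case against is that little is actually lost. Four parts of it deserve weight.

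- **The group is narrow.** A reader might infer that everyone who stops drug loses AVT follow-up. The text does not support that: full follow-up is the default, and only those who also cannot comply move to the list. A mandatory stop for Grade 3 reactogenicity does not by itself put anyone there. This stands.
- **The list may be a minimum request and not a cap.** The general rules still call for AVT to 1 year, and 5.5.6 covers SAEs that are observed or spontaneously reported. It would go too far to say that SAE collection ends at 30 days. Even so, the list is the specific instruction for this group, and its horizon differs from the general one without explanation.
- **AVT can be recovered.** AVT starts are dated treatments found in medical records. V14 is offered, the health economic data come from retrospective record review that includes concomitant medications (Protocol 5.3.8.4), and section 5.1.5.2 collects late medication for adjudicated events. For the same reason, different censoring rules for AVT and viremia are not inconsistent in themselves. Some AVT would be recovered, but nothing in 3.5 asks for it, V14 attendance is voluntary, and Table 1 footnote 6 omits the adjudicated-event medication that 5.1.5.2 includes.
- **Direction.** A reader might infer that the error favours ASP0113, because phase 2 local reactogenicity was 22.9% against 10.9%. Those are reactions of any grade; they are not drug stops or inability to attend. Inability to attend may equally follow illness, and phase 2 deaths and severe GVHD were numerically higher on placebo (Protocol Table 3, none significant). The direction is unknown.

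**Conclusion.** The point holds as a narrow, inexpensive improvement. The reduced list leaves out a key secondary endpoint that the protocol otherwise collects to 1 year, and SAP 7.4.2.2 and 7.4.2.3.2 can turn the resulting gap into AVT-free time. Separately, the 30-day SAE horizon, the 1-year rules in Protocol 5.4.2 and 5.5.6, and the TEAE window in SAP 6.2 must be reconciled.

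The primary endpoint is not affected: EOD and mortality stay on the list, and unknown survival counts as an event.

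The size rests on assumptions. Equal loss at 5% to 10% of each arm, with half of AVT starts missed, costs 1.5 to 3.2 points of power (91.6% to 90.1% or 88.4%); the worst case in the grid is 76.3%. Loss confined to one arm gives spurious hazard ratios from 0.99 to 0.80 in that arm's favour, depending on the share and on how early ascertainment stops. The earlier and larger losses are the extreme end. The calculations also assume that no missed AVT is recovered from records or at V14, beyond the fraction u in the power table.

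**What to change.** 1. **Protocol 3.5 and synopsis.** Add to the reduced list: *start of any CMV-specific AVT, with date and reason, obtained by telephone or medical record review through day 365*.
2. **SAE horizon.** Reconcile the 30-day item with sections 5.4.2 and 5.5.6 and the SAP window, and state which applies to subjects on reduced follow-up.
3. **SAP 7.4.2.2.** Censor subjects without AVT at the last date on which AVT status was ascertained. In **7.4.2.3.2**, use the last date on which both AVT and EOD status were ascertained. State how a death after ascertainment has lapsed is handled, because the model treats death as a competing event.
4. **CMH analyses involving AVT (7.4.2.2, 7.4.2.3.1, 7.4.2.3.2).** State how incomplete AVT ascertainment is classified, report the number of such subjects by arm, and add a sensitivity analysis, for example excluding them and then counting them as events. This is needed even with the new censoring date, since subjects who leave the schedule may differ in AVT risk.

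The cost is one record-review item for this group, a recorded date of last AVT ascertainment, and a few sentences in the SAP. The downside is slightly shorter AVT follow-up time for the affected subjects.
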